##### **6.1.2.2. Duration**

The present study tests the hypothesis that 4 weeks of continuous subcutaneous infusion of low dose glucagon will increase counter regulatory hormone response to insulin induced hypoglycemia. This is consistent with the finding that scrupulous avoidance of hypoglycemia has been demonstrated to partially restore autonomic responses to hypoglycemia in this population.

To obtain preliminary data describing the duration of such response, subjects are retested 3 and 6 months after the cessation of the investigational product.

### **6.1.2.3. Glucagon Infusion Rate Selection**

A previous study (Edelman, ADA annual scientific sessions, 2006) evaluating continuous glucagon administration for the prevention of hypoglycemia tested doses at 2, 4 and 8 ng/(kg\*min) and found apparently no effect at 2 ng/(kg\*min), weak indications of effect at 4 ng/(kg\*min) and, given a modest sample size, reasonably clear effect at 8 ng/(kg\*min) with some but limited room for further effect.

These findings would suggest doses in the vicinity of 4 and 16 ng/(kg\*min) corresponding to 19.2 and 76.8 µg/hr for an 80-kg person would be well chosen in this proof-of-concept study. As further development would most likely lead to a device with a fixed infusion rate, the glucagon doses chosen for the study are 20 and 80 µg/hr, or given the formulation concentration of 5 mg/ml, infusion rates of 4 and 16 µl/hr. For the pump setting that measures in insulin U100 units that corresponds to 0.4 and 1.6 U/hr.

This highest dose to be tested in the study will allow a greater than 10x safety margin based on findings from a 28-day toxicology study in rats conducted with Xeris glucagon (see current Investigator's Brochure).

### **6.1.2.4. Insulin Dose Adjustments**

Constant infusion of low rate of glucagon may be expected to elevate glucose not only during circumstances that may have led to hypoglycemia, but also when not needed. To avoid glycemic escape, subjects' glucose data will be reviewed weekly and insulin doses adjusted accordingly by the clinical personnel.

### **6.1.2.5. Hypoglycemia induction**

The hypoglycemia induction using a high continuous IV insulin infusion rate countered by a continuous IV glucose infusion is standard for HAAF protocols as published in a substantial body of literature. The planned insulin infusion rate of 20 mU/(BSA\*min) is somewhat smaller than what is used in other studies but is still a sufficiently high rate to bring most subjects into hypoglycemia.

## **6.2. Non-Clinical Pharmacology and Toxicology Experience with Glucagon**

Native glucagon for injection (bovine, porcine origin) was approved for use in humans in 1960 [FDA CDER #1]. The 29 amino acid sequence of pancreatic glucagon is identical in humans, cows, pigs, dogs, and rats, and is also conserved in biosynthetic versions of glucagon [Eistrup]. Glucagon for injection (rDNA origin) was approved in 1998 and is currently the subject of two approved NDAs ([NDA 20-928] and [NDA 20-918]). Complete NDA-required pharmacology and toxicology data have been reviewed and accepted by the FDA, as described in Lilly Glucagon [rDNA origin] for injection and Novo GlucaGen® (glucagon [rDNA origin] for injection) labeling [Glucagon, Glucagen]. As Xeris' drug product is produced by solid-phase peptide synthesis (SPPS), which also conserves the glucagon peptide sequence, the rDNA

glucagon information is pertinent to the development of Xeris' glucagon formulation. A summary of this information can be found in Xeris' current Investigator's Brochure, which will be provided to each investigator participating in this study.

#### **6.2.1. Nonclinical Pharmacology and Toxicology of Xeris Investigational Non-Aqueous, Synthetic Glucagon**

Information on the nonclinical pharmacology, pharmacokinetics and toxicology of Xeris' glucagon formulation is referenced to Xeris' current Investigator's Brochure.

#### **6.3. Description and Composition of Drug Product**

Synthetic glucagon is the drug substance in Xeris' glucagon formulation. Glucagon cGMP grade is manufactured, packaged and released by Bachem AG (Bubendorf, Switzerland), conforms with USP standards and has a Type II DMF filed with the FDA. Xeris' glucagon formulation is a sterile subcutaneous injectable non-aqueous formulation for treatment of severe hypoglycemia. Xeris' glucagon formulation contains 5 mg/ml of glucagon, with trehalose and DMSO as excipients. Xeris' glucagon formulation is supplied in 1.0 mL vials. The drug product is stored at controlled room temperature (20-25°C) prior to use.

#### **6.4. Clinical Experience with Glucagon**

Glucagon has a long history of medical use in the US, and is currently marketed by Eli Lilly & Co. as Glucagon (Glucagon Injection [rDNA origin]), and Novo Nordisk as GlucaGen® HypoKit®, both RLDs for treatment of severe hypoglycemia. Glucagon has a rapid onset of action and an extremely short half-life, and its safety, efficacy and clinical pharmacology have been well established [[FDA CDER #2](#)]. The Agency first approved glucagon for use in humans in 1960.

[figure not shown]
Since 2013 when the first IND for Xeris formulation went into effect, multiple clinical studies have been successfully completed including two studies utilizing the Omnipod for delivery. Details are provided in Xeris' current Investigator's Brochure.

## 7. STUDY DESIGN

### 7.1. Study Overview

This is a prospective, randomized, double-blind, parallel trial with the primary analysis after 4 weeks treatment with CSGI or placebo. As both the low and high dose group use the same formulation, the dose will be determined by infusion. To preserve the blind, the placebo therefore is administered by matching infusion methods to CSGI (high and low infusion rates, split to create the appearance of a 4-group trial on the schematic).

Study Schematic:

After a 1-week run-in on CGM, subjects will have key hormones of their hypoglycemia counter regulatory response quantified using a stepwise hypoglycemia induction. They will then receive investigational product for 4 weeks before discontinuation and reassessment of the same hypoglycemia counter regulatory response.

Treatment stops at 4 weeks, but subjects will continue blinded for 6 additional months to investigate duration of response with assessments at 3 and 6 months. The primary endpoint will be tested at 4 weeks post randomization, but the double blind will remain intact until the end of the study.

Baseline Qualification:

Subjects will continue their insulin regimen as usual throughout the study, adjusted by the investigator to achieve ADA recommended targets.

After enrollment, the subjects will require approximately one week of CGM data prior to their baseline hypoglycemia induction procedure. Subjects will enter a run-in phase of 1 week wearing a blinded CGM device.

Subjects will arrive in the Clinical Research Unit (CRU) the morning of the planned hypoglycemia induction procedure. The CGM data will be retrieved. The following CGM criteria must be met: a minimum of 6 days must be recorded using the CGM before the subject will be fitted with a new CGM device. If the CGM criteria are not met, the subject is inserted with another CGM for renewed baseline period. Should the second baseline period not yield eligible CGM data, the subject will stop further participation in the screening procedures.

The subject will fast after midnight. The subject's arms are cannulated venously, one side for both insulin and glucose infusion and the other side for venous sampling. The subject will stop their own insulin treatment and receive IV insulin and IV glucose to maintain their plasma glucose between 80 to 120 mg/dL, as measured by either BGM or YSI. They will remain fasting until the end of the hypoglycemia procedure the following day.

Hypoglycemia induction procedure:

In the morning, insulin induced hypoglycemia ( $PG < 50$  mg/dL as measured by YSI) is achieved through a hyperinsulinemic clamp procedure.

The plasma glucose should be verified to be between the 80-120 mg/dL. The IV insulin infusion rate is then increased to  $20 \text{ mU}/(\text{body surface area (BSA)} \cdot \text{min})$  as a set rate and the subject's plasma glucose is stabilized at  $100 \pm 10$  mg/dL for minimally 60 minutes, through adjustments in continuous IV glucose. After this 60-minute stable period, the plasma glucose will be reduced to 70 mg/dL by decreasing the continuous IV glucose infusion rate. When the plasma glucose has been stable at  $70 \pm 5$  mg/dL for 20 minutes, a hypoglycemia symptom questionnaire administered, which will be repeated after 10 minutes.

The hypoglycemia induction will then begin, decreasing the continuous IV glucose infusion rate to bring the plasma glucose down to  $< 50$  mg/dL. Plasma glucose is measured every 5 minutes and the continuous IV glucose infusion rate is adjusted to achieve the target glucose concentration of  $< 50$  mg/dL. Hypoglycemia assessment will be administered every five minutes from this point until the end of the induction and PG recovery phase. When the target plasma glucose of  $< 50$  mg/dL has been achieved, blood samples for the assessment of counter regulatory hormones are drawn. Plasma glucose concentration will be measured and maintained at  $50 \pm 5$  mg/dL for 30 minutes after which another set of blood samples for the assessment of counter regulatory hormones are drawn and the hypoglycemia questionnaire re-administered. The insulin infusion is then stopped, and plasma glucose is raised to  $> 70$  mg/dL through the continuous IV glucose. The continuous IV glucose infusion is stopped once the subject's  $PG > 70$  mg/dL and the subject will be given a standardized meal. The subject is monitored until deemed medically stable for discharge, per investigator discretion.

Visit Overview:

After the completion of the first study visit (the baseline hypoglycemia induction procedure), the investigator will train the subjects to load, prime, and use the modified OmniPod. In this training, the subject will learn to prepare and use an OmniPod at a suitable infusion site. This includes direct observation of the subject when they attach and initiate the device, by the investigational staff.

The subject is then randomized to a study treatment and begins therapy in the CRU. The assigned study treatment will be 4 weeks in duration. They are initially provided with a 1-week supply of blinded study drug and OmniPods. The subjects will return weekly for a safety check, CGM device data retrieval, new sensor insertion, and receipt of study supplies. The subject is expected to complete at least 90% of the study therapy during the 4-week treatment period.

After 4 weeks of study therapy, the subject will return to the clinic. The study product will be stopped and the CGM data retrieved before a repeat of the hypoglycemia induction procedure as described above.

After 12 weeks after study treatment, the subjects will return to the CRU for insertion of a CGM device. One week later (13 weeks after completing study treatment), the CGM will be retrieved and the subject will undergo the hypoglycemia induction procedure as described above.

After 25 weeks after study treatment, the subjects will return to the CRU for insertion of a CGM device. One week later (26 weeks after completing study treatment), the CGM will be retrieved and the subject will undergo the hypoglycemia induction procedure as described above.

After completion of the hypoglycemia induction procedure at 26 weeks, the subject's participation in the study is completed.

## **7.2. Interruption and Termination of Dosing**

Dosing will be paused for any SAE that occurs in a subject receiving treatment until causality is fully assessed by the Investigator. Dosing will cease if the SAE is determined to be either drug-related or unknown, and may resume if the SAE is determined to be not drug-related by the investigator and the Sponsor agrees.

## **8. ELIGIBILITY CRITERIA AND STUDY ENROLLMENT**

Subject eligibility should be reviewed and documented by an appropriately qualified member of the investigator's study team before a subject is included in the study. Subjects must meet the following inclusion and exclusion criteria to be eligible for enrollment into the study.

### **8.1. Inclusion Criteria**

1. Males or females diagnosed with type 1 diabetes mellitus for at least 24 months.
2. Random serum C-peptide concentration < 0.6 ng/ml at Screening.
3. Age 21-64 years, inclusive, at screening.
4. Documented Hypoglycemia unawareness as evidenced by a Gold Scale score  $\geq 4$ , at screening
5. Medical history of an episode of severe hypoglycemia as reported by patient < 50 mg/dL, in the 1 year prior to screening.
6. Current use of multiple daily dosing insulin treatment (< 1 U/(kg\*day) total daily dose) either administered with subcutaneous injections or continuous subcutaneous insulin infusion (CSII).
7. Performs monitoring of glucose minimally 3 times a day. Patients using continuous glucose monitoring for monitoring should continue to do so during the course of the study.
8. Willingness to provide informed consent and follow all study procedures, including using the Medtronic smartphone application "iPRO2mylog" for diabetes data logging and attending all scheduled visits.

### **8.2. Exclusion Criteria**

1. HbA1c  $\geq 10\%$  at Screening.
2. Chronic kidney disease stage 4 or 5.
3. Hepatic disease, including serum ALT or AST greater than or equal to 3 times the upper limit of normal; hepatic synthetic insufficiency as defined as serum albumin < 3 g/dL.
4. Hematocrit of less than or equal to 30% at Screening.
5. BP reading at Screening where SBP <90 or >150 mm Hg, or DBP <50 or >100 mm Hg.
6. Clinically significant ECG abnormalities at Screening.
7. Congestive heart failure, NYHA class III or IV
8. History of myocardial infarction, unstable angina or revascularization within the past 6 months.
9. History of a cerebrovascular accident with residual neurologic deficit.

10. Current seizure disorder, unrelated to hypoglycemia.
11. History of pheochromocytoma or disorder with increased risk of pheochromocytoma (MEN 2, neurofibromatosis, or Von Hippel-Lindau disease).
12. History of insulinoma.
13. Active malignancy within 5 years from Screening, except basal cell or squamous cell skin cancers. Any history of breast cancer or malignant melanoma will be exclusionary.
14. Major surgical operation within 90 days prior to Screening.
15. Current bleeding disorder, treatment with anticoagulants, or platelet count below 50,000/mL at Screening.
16. History of allergies to glucagon or glucagon-like products, or any history of significant hypersensitivity to glucagon or any related products or to any of the excipients (DMSO, trehalose) in the investigational formulation.
17. History of glycogen storage disease.
18. Any concurrent illness, other than diabetes, that is not controlled by a stable therapeutic regimen.
19. Active substance or alcohol abuse (more than 21 drinks/wk. for males or 14 drinks/wk. for females). Subjects reporting active marijuana use and/or testing positive for THC via rapid urine test will be allowed to participate in the study at the discretion of the investigator. Subjects positive for other drugs of abuse via rapid urine test who report use of a prescription or OTC medication that would explain such a finding will be allowed to participate at the discretion of the investigator.
20. Administration of glucagon within 7 days of Screening.
21. Pregnant and/or Lactating. For subjects of childbearing potential, there is a requirement for a negative urine pregnancy test and for agreement to use contraception and to refrain from breast feeding during the study and for at least 1 month after participating in the study. Acceptable contraception includes birth control pill / patch / vaginal ring, Depo-Provera, Norplant, an IUD, the double barrier method (the female uses a diaphragm and spermicide and the male uses a condom), or abstinence.
22. Inadequate venous access.
23. Participation in other studies involving administration of an investigational drug or interventional device within 30 days or 5 half-lives, whichever is longer, before Screening for the current study and during the four weeks of study product administration in the current study.
24. Any reason the principal investigator deems exclusionary.

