Inclusion Criteria:	
 
1. Males or females diagnosed with type 1 diabetes mellitus for at least 24 months.
 
2. Random serum C-peptide concentration < 0.6 ng/ml at Screening.
 
3. Age 21-64 years, inclusive, at screening.
 
4. Documented Hypoglycemia unawareness as evidenced by a Gold Scale score <math>\geq 4</math>, at screening
 
5. Medical history of an episode of severe hypoglycemia as reported by patient < 50 mg/dL, in the 1 year prior to screening.
 
6. Current use of multiple daily dosing insulin treatment (< 1 U/(kg*day) total daily dose) either administered with subcutaneous injections or continuous subcutaneous insulin infusion (CSII).
 
7. Performs monitoring of glucose minimally 3 times a day. Patients using continuous glucose monitoring for monitoring should continue to do so during the course of the study.
 
8. Willingness to provide informed consent and follow all study procedures, including using the Medtronic smartphone application “iPRO2mylog” for diabetes data logging and attending all scheduled visits.
 

Exclusion Criteria:	
 
1. HbA1c <math>\geq 10\%</math> at Screening.
 
2. Chronic kidney disease stage 4 or 5.
 
3. Hepatic disease, including serum ALT or AST greater than or equal to 3 times the upper limit of normal; hepatic synthetic insufficiency as defined as serum albumin < 3 g/dL.
 
4. Hematocrit of less than or equal to 30% at Screening.
 
5. Clinically significant ECG abnormalities at Screening.
 

6. Congestive heart failure, NYHA class III or IV.
7. History of myocardial infarction, unstable angina or revascularization within the past 6 months.
8. History of a cerebrovascular accident with residual neurologic deficit.
9. Current seizure disorder, unrelated to hypoglycemia.
10. History of pheochromocytoma or disorder with increased risk of pheochromocytoma (MEN 2, neurofibromatosis, or Von Hippel-Lindau disease).
11. History of insulinoma.
12. Active malignancy within 5 years from Screening, except basal cell or squamous cell skin cancers. Any history of breast cancer or malignant melanoma will be exclusionary.
13. Major surgical operation within 90 days prior to Screening.
14. Current bleeding disorder, treatment with anticoagulants, or platelet count below 50,000/mL at Screening.

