**Waivers to the inclusion/exclusion criteria will not be granted**

### **8.3. Enrollment**

Screening will continue until 48 subjects are qualified and randomized for the study. Subjects will not be considered enrolled in the study until the time of randomization

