### **8.10. Concomitant Medications**

Subjects should be on a stable dose of all concomitant medications for at least 30 days prior to Screening. All subjects must have their concomitant medications reviewed at each visit. Medications taken within 4 weeks before Day 1 will be documented in the CRF. Any changes to a subject's concomitant medication regimen will be documented. Investigators are encouraged to avoid adding to or changing a participant's medications until week 4 of study participation unless deemed medically necessary.

There are not medications that are specifically prohibited during participation in this study, except the medications (e.g., anticoagulants) listed under the exclusion criteria (see Section 8).

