**Table 7: Frequency and Volume of Blood Collections**

Assay	Sample Volume (mL)	Screening	V3	V7	V9	V11	Total (mL)
Plasma Glucose (YSI)*	2		50	50	50	50	400
Serum Ethanol	5	1					5
Chemistry (14 gen chem. incl. ALT, AST, bilirubin, albumin)	7.5	1	1	1		1	30
C-peptide, serum	2.5	1					2.5
Hematology (Hemoglobin, Hematocrit, Platelet Count, MPV, RDW, RBC Count, WBC Count, MCV, MCH, MCHC, - no differential)	3.5	1	1	1		1	14
HbA1c (included in hematology)		1					0

Assay	Sample Volume (mL)	Screening	V3	V7	V9	V11	Total (mL)
Hormone levels: Cortisol, Norepinephrine, Growth hormone	2		4	4	4	4	32
Hormone levels: Plasma epinephrine	4		4	4	4	4	64
Glucagon	8.5		4	5	4	4	144.5
Immunogenicity (Anti-glucagon antibody)	3.5	1		1	1	1	14
Total/Visit (mL)		22	169	181	161.5	172.5	706

a Single PG measurements at bedside via rapid glucose analyzer.

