**Table 8: Clinical and Safety Related Laboratory Tests Performed at Site**

Hematology	CMP/Metabolic	Urine
WBC count	Ca ++	β-hCG a
RBC count	Random Glucose	Drug screen b
Hemoglobin	Albumin	
Hematocrit	Na +	
Platelet count	K +	
MPV	Total Protein	
RDW	Bicarbonate	
MCV	Chloride	
MCH	BUN	
MCHC	Creatinine	
(no differential)	Alkaline Phosphatase	
	AST/SGOT	
	ALT/SGPT	
	Bilirubin	

Hormones	Immunogenicity	Laboratory
Growth	Anti-glucagon-antibody	HbA1c
Cortisol		C-peptide
Epinephrine		HIVab
Norepinephrine		HCVab
Glucagon		HBsAg

a Female participants of childbearing potential require a negative pregnancy test at Screening. Pregnancy testing will be repeated at the last treatment visit.

b Drug screening performed at Screening and the 2 Treatment Visits will include: cocaine, THC, opiates, benzodiazepines, and amphetamines. Except as noted below, inclusion in the study requires all tests to be negative at screening with the exception of THC, which will be noted, but will not be considered exclusionary.

A central laboratory will be utilized for analysis of all variables with the exception of urine tests, and rapid PG measurements made during treatment visits. A procedures manual will be provided to each site by the central laboratory. This manual will cover procedures for the collection, processing and shipping of blood samples, along with the Clinical Laboratory Improvement Act (CLIA) certification and normal ranges for the central laboratory.

The central laboratory will provide sites with all supplies needed for collection, processing and shipping of all blood samples, including PK samples, as well as point-of-care urine pregnancy tests.

Rapid urine drug screen kits will be provided to the sites. If a subject tests positive for other than THC at screening, the subject will normally be excluded from further study participation. However, if subject reports use of a concomitant medication (prescription or OTC) that provides a reasonable explanation for a positive result other than THC, the subject may be allowed to participate in the study at the investigator's discretion. If the subject is not able to provide a reasonable explanation but still refutes a positive finding, a urine sample will be sent to the central laboratory for confirmation. The result of this confirmatory test will be considered definitive.

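### The platelet limit in exclusion 15 (synopsis no. 14) is written per mL, which is 50 per microlitre, so that part of the criterion excludes nobody at any plausible count

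*Protocol*

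**What the plan says.** Exclusion 15 in Protocol Section 8.2 reads "Current bleeding disorder, treatment with anticoagulants, or platelet count below 50,000/mL at Screening". The synopsis has the same criterion as no. 14, again with "platelet count below 50,000/mL at Screening". The numbers differ only because Section 8.2 carries an extra blood pressure criterion (no. 5). No other place in the protocol or SAP states a platelet limit.

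The criterion is binding. The opening of Section 8 makes meeting all criteria a condition of enrollment, and the line just before Section 8.3 adds: "Waivers to the inclusion/exclusion criteria will not be granted".

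The platelet count is measured. It belongs to the hematology panel in Tables 7 and 8, and Table 7 shows that panel drawn at screening. Neither table gives a reporting unit or a reference range. Section 10.2 leaves the "normal ranges for the central laboratory" to a laboratory manual that is not part of the documents.

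Two further passages bear on the point. Section 8.10 relies on the exclusion criteria to keep anticoagulants out of the trial. The last exclusion in Section 8.2 (no. 24) is "Any reason the principal investigator deems exclusionary".

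**The concern.** A limit of 50,000 per mL is far below any count that a patient would plausibly show. Read as written, the comparison of a screening result with this limit never excludes a subject.

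The limit is a decision rule that is meant to be applied to each screening result. A site that applies the text literally has no platelet check. A site that silently reads another unit applies a rule that the protocol does not contain. The two sites could decide differently on the same result, and a monitor could verify neither decision cleanly against the protocol.

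The rule also has a place in the analysis documents. SAP Section 7.1.2 requires per-protocol subjects to satisfy every inclusion and exclusion criterion, and SAP Listing 16.2.1.2 reports the eligibility assessment.

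The procedures explain why a platelet limit was set at all. Both arms are cannulated at each hypoglycemia induction, and inductions are scheduled at Visits 3, 7, 9 and 11. Table 7 totals 706 mL of blood over the study. Subjects place a new pod every 2 to 3 days for 4 weeks.

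**Working it through.** The limit is a threshold with no derivation in the documents, so there is no plan figure to reproduce. The check is a unit conversion followed by a comparison with assumed counts.

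**Inputs from the documents**
- Limit: below 50,000 per mL (Section 8.2 no. 15; synopsis no. 14).
- Structure of the criterion: the platelet part follows "Current bleeding disorder, treatment with anticoagulants, or", so any one of the three parts excludes on its own.

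**Input assumed**
- Platelet counts of 10 to 450 x 10^9/L. The documents give no range.

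**Step 1: convert the written limit**
- 1 mL = 1,000 microlitres, so 50,000 per mL / 1,000 = 50 per microlitre.
- 1 L = 1,000 mL, so 50,000 per mL x 1,000 = 50,000,000 per L = 0.05 x 10^9/L.

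**Step 2: compare assumed counts with the limit**

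Ratio = (count per microlitre x 1,000) / 50,000.

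| Assumed count (10^9/L) | Per microlitre | Per mL | Ratio to written limit | Excluded as written? |
|---|---|---|---|---|
| 10 | 10,000 | 10,000,000 | 200 | No |
| 20 | 20,000 | 20,000,000 | 400 | No |
| 50 | 50,000 | 50,000,000 | 1,000 | No |
| 150 | 150,000 | 150,000,000 | 3,000 | No |
| 450 | 450,000 | 450,000,000 | 9,000 | No |

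For the platelet part to exclude anyone, the count would have to fall below 0.05 x 10^9/L, which is 1/200 of the lowest count in the table. The result therefore does not depend on where the assumed range is drawn.

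**Step 3: the size of the unit question**

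The same number expressed per microlitre is 50,000 x 1,000 = 50,000,000 per mL = 50 x 10^9/L, exactly 1,000 times the written limit. At that value the counts of 10 and 20 x 10^9/L would be excluded and the other three would not. This shows only that the unit decides whether the rule does anything. It does not say which limit is right.

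**Step 4: what remains of the criterion**

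The bleeding-disorder and anticoagulant parts contain no number and are unaffected. Section 8.10 depends on the anticoagulant part, which works as intended.

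**The case against.** The strongest reply is that this is a typographical slip with little practical consequence, and much of that reply stands.

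- **The criterion is not empty.** A reader might infer that the bleeding-risk exclusion as a whole can exclude nobody. The text does not support that, because two of its three parts operate fully.
- **There are backstops.** A known platelet disorder may count as a bleeding disorder. Exclusion 18 covers illness that is not controlled on a stable regimen, and exclusion 24 lets the investigator exclude for any reason. Section 9.5.1 has a study investigator assess the criteria, with the final decision after the laboratory results. It therefore does not follow that a subject with a very low count would be enrolled. The no-waiver statement does not change this, since it stops sites admitting subjects who fail a criterion and does not limit exclusion on other grounds. Discretion is nevertheless not a substitute for a stated threshold, because it is unspecified and can differ between sites.
- **No automated check is described.** A reader might suppose that a programmed eligibility check would pass everyone. The documents describe review by people, and any such check is speculation.
- **The analysis is not shown to be affected.** Few or none of the 48 subjects may have a count at which the unit matters. The link through SAP Section 7.1.2 means only that the criterion is one of those that define the per-protocol set. It does not show that membership would change.
- **The unit might be an artefact of reading the PDF.** A lost micro sign would produce this text. That is possible but unlikely: the unit is the same in both places, and Section 6.1.2.3 of the same file keeps its micro signs in the infusion rates.

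**Conclusion.** The point holds for the platelet part of the criterion only. As written in both places, the limit equals 50 per microlitre (0.05 x 10^9/L), and it excludes nobody across assumed counts of 10 to 450 x 10^9/L, which lie 200 to 9,000 times above it. The conversion is exact. The conclusion that nobody is excluded rests on the assumed range, though it would survive any reasonable choice of that range.

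Two things are not established. The documents agree with each other on this limit, so they do not show what unit or value was intended; that a different unit was meant is likely but remains an inference. Nor is there any demonstrated effect on sample size, power, alpha or the primary analysis. What is established is that a numeric safety exclusion, binding and without waivers, does nothing as it stands, and that sites can reasonably apply it in different ways. That justifies a correction, at modest priority.

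**What to change.** The sponsor, with the medical monitor, should confirm the intended unit and the intended limit. Both should then be stated identically in synopsis exclusion 14 and Section 8.2 exclusion 15, in the unit in which the central laboratory reports platelets, so that sites compare like with like. If an eCRF eligibility check on this item exists, it should use the same unit and limit. The value is the sponsor's decision, and none is proposed here.

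The cost is a short textual change in two places and the alignment of any eCRF check. Section 16.1 requires IRB approval of protocol modifications, so the change is best carried in the next amendment. The SAP needs no change, because Section 7.1.2 refers to the criteria without restating them. No new data are needed, as the platelet count is already measured at screening. The only subjects affected in recruitment are those whom the confirmed limit is meant to exclude.
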